7.2. Clinical Laboratory Tests

7.2.1. Chemistry

A summary table of descriptive statistics will be presented for the observed values and the change from baseline for chemistry parameters by time point. A listing of laboratory chemistry parameters will be provided.

7.2.2. Hematology

A summary table of descriptive statistics will be presented for the observed values and the change from baseline for hematology parameters by time point. A listing of laboratory hematology will be provided.

7.2.3. Coagulation

A summary table of descriptive statistics will be presented for the observed values and the change from baseline for activated partial thromboplastin, partial thromboplastin time, prothrombin time, and international normalized ratio by time point. Coagulation parameters will be listed.

7.2.4. Viral Shedding

Viral shedding results recorded as below limit of quantification (BLOQ) or below limit of detection (BLOD) will be classified as “Not Detected” and any positive value will be recorded as

“Detected”. A shift table will be provided to display shift from baseline of “Detected” and “Not Detected” values. A listing of viral shedding results from blood, urine and CSF will be provided.

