^e If historic enzyme results are available, they may be used to determine eligibility. If historic enzyme results are used to determine eligibility, enzyme testing does not need to be repeated at Screening.

^f Analyzed by a Central Laboratory.

^g Subjects must pre-consent and have a negative COVID-19 test prior to the Screening Visit. Subject must test negative for COVID-19 a maximum of 72 hours prior to receiving gene therapy. If a subject tests positive for COVID-19 at the Screening or Baseline Visit, he/she will need to have negative test results for 2 weeks (2 weeks since the last positive test result and 2 negative test results a minimum of 14 days apart, with the second negative test result no more than 72

hours prior to surgery) before receiving gene therapy. If a COVID-19 test is administered per site policy within 72 hours of the Screening Visit, the results may be used for the AADC-GT-002 study. The COVID-19 test does not need to be repeated after the COVID-19 pre-consent is signed.

^h Females of childbearing potential only. The pregnancy test can be collected via urine or serum, at the discretion of the PI. Will be assessed by a local laboratory.

ⁱ CSF analysis history (check only HVA/5-HIAA/3-OMD/pterins/MHPG/L-DOPA/5-HTP) to be collected if available.

^j Subjects may be admitted to the hospital and sedation may be used at the discretion of the PI.

^k CSF analysis items (HVA/5-HIAA/3-OMD and cell count [appearance, RBC, WBC, protein, and glucose]).

^l Sample should be collected predose on day of surgery.

^m CSF sample will be collected predose during the surgical procedure for the purposes of assessing viral shedding and neurotransmitter analysis.

ⁿ Urine should be collected using a clean catch or catheter and stored in a sterile container.

^o Days that require imaging or lumbar puncture can be split into 3-day visits, if necessary, provided that all clinical assessments (Bayley-III, EQ-5D-Y, and PDMS-2) are completed prior to any other assessments on Days 1, 2, or 3 of the visits.

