1. LIST OF ABBREVIATIONS

Table 1: List of Abbreviations

Abbreviation	Term
¹⁸ F-DOPA	L-6-[¹⁸ F] fluoro-3,4-dihydroxyphenylalanine
3-OMD	3-O-methyldopa
5-HIAA	5-hydroxyindoleacetic acid
AADC	Aromatic L-amino acid decarboxylase
AE	Adverse Events
AESI	Adverse Event of Special Interest
ATC	Anatomical, Therapeutic, and Chemical
Bayley-III	Bayley Scale Infant development, third edition
BLOD	Below limit of detection
BLOQ	Below limit of quantification
BMI	Body mass index
CRF	Case Report Forms
CS	Clinically Significant
CSF	Cerebrospinal Fluid
CTCAE	Common Terminology Criteria for Adverse Events
DDC	DOPA Decarboxylase (gene)
DSMB	Data Safety Monitoring Board
eCRF	Electronic Case Report Form
ECG	Electrocardiogram
ET	Early Termination
HVA	Homovanillic Acid
ICF	Informed Consent Form
IEC	Independent Ethics Committee
IRB	Institutional Review Board
LLOQ	Lower limit of quantification
MedDRA	Medical Dictionary for Regulatory Activities
MR	Magnetic resonance
MRI	Magnetic Resonance Imaging
NCS	Non-clinically Significant
OGC	Oculogyric Crisis
PD	Pharmacodynamic
PDMS-2	Peabody Developmental Motor Scale, second edition
PET	Positron Emission Tomography
PT	Preferred Term
QTcB	Bazett corrected QT measurement
QTcF	Fridericia corrected QT measurement
SAE	Serious Adverse Events
SAP	Statistical Analysis Plan
SOC	System Organ Class
TEAE	Treatment Emergent Adverse Events
TEAESI	Treatment Emergent Adverse Event of Special Interest
TESAE	Treatment Emergent Serious Adverse Events
vg	Vector genome
WHO	World Health Organization

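### SAP 7.2.4 reports viral shedding results below the quantification limit as not detected, although such a result does not establish that vector is absent

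*SAP*

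**What the plan says.** SAP section 7.2.4 (Viral Shedding) sets a two-way classification:

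- "Viral shedding results recorded as below limit of quantification (BLOQ) or below limit of detection (BLOD) will be classified as" *Not Detected*.
- In the same sentence, "any positive value will be recorded as" *Detected*. The term positive value is not defined.
- "A shift table will be provided to display shift from baseline of" these two categories. This is the only shedding summary that the SAP specifies.
- "A listing of viral shedding results from blood, urine and CSF will be provided".

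The SAP's list of abbreviations expands the two acronyms separately, as "Below limit of detection" and "Below limit of quantification". It does not say what a result between the two limits is called.

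The baseline sample is taken before dosing in all three sample types. For blood and urine, protocol Table 1 says: "Sample should be collected predose on day of surgery". For CSF it says: "CSF sample will be collected predose during the surgical procedure for the purposes of assessing viral shedding and neurotransmitter analysis". Protocol section 4.2 excludes anyone previously treated with a gene therapy. Table 1 also states that shedding samples are analysed by a central laboratory.

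Protocol section 7.5.11 gives the purpose of the shedding assessment: to find any possible exposure risk to people in contact with the subject. Protocol section 8.3.3 plans a by-visit summary of shedding, with shift tables where appropriate, and gives no rule for results below either limit.

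**The concern.** The limit of detection concerns whether vector can be found at all. The limit of quantification concerns whether the amount can be measured reliably. An assay with both limits can return a result that lies between them: vector is present, but the amount is too low to report as a number. Many readers would expect BLOQ to denote that result, and section 7.2.4 calls it *Not Detected*.

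For a measure of drug exposure, grouping low values with absent values may do little harm. Here the stated purpose is exposure risk to contacts, so whether vector was found is itself of interest. A table that merges the two states could show no new shedding where some was found, or show shedding ending earlier than it did.

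The undefined term adds a smaller uncertainty. Someone coding a result that the laboratory calls positive but below the LOQ is not told what counts as a positive value.

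**Working it through.** The plan states no figure on this point to reproduce. The check maps each possible change in result under the SAP rule and under a rule that keeps BLOQ separate.

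**Inputs**

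- SAP rule: BLOD and BLOQ go to *Not Detected* (ND); a quantified result goes to *Detected* (D). Source: SAP 7.2.4.
- Expected baseline: no vector. Source: predose sampling in protocol Table 1 and the prior gene therapy exclusion in protocol 4.2.
- Minimum number of subjects: 3. Source: SAP 2.4.
- Assay limits and the meaning of BLOQ: not given. Both possibilities are examined.

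**Case A (assumption): the assay has an LOD, and BLOQ means detected but not quantifiable**

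| Change | SAP rule | BLOQ kept separate |
|---|---|---|
| BLOD to BLOD | ND to ND | ND to ND |
| BLOD to BLOQ | ND to ND, no shift | ND to BLOQ, shift |
| BLOD to quantified | ND to D, shift | ND to D, shift |
| Quantified to BLOQ | D to ND, looks cleared | D to BLOQ, still present |
| Quantified to BLOD | D to ND, cleared | D to ND, cleared |

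A quantified baseline is not expected, so the fourth row matters mainly across successive visits. A subject counted as D at one post-dose visit and BLOQ at the next returns to ND in the later table, if the shift table is produced by visit.

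**Case B (assumption): the assay reports against the LOQ only**

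BLOD does not occur. The baseline would be BLOQ, and BLOQ to BLOQ shows no shift under either rule. No table cell count changes. The label is still wrong, because a result known only to be below the LOQ does not show that nothing was detected.

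**Case C (assumption): BLOQ never contains detectable vector**

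The SAP rule misclassifies nothing.

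**Size per result in Case A**

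Let k be the number of subjects who go from BLOD to BLOQ, out of 3, for one sample type and visit, with the remaining subjects BLOD. The SAP table shows 0/3 = 0% detected. The share with vector found is k/3:

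- k = 0: 0/3 = 0%
- k = 1: 1/3 = 33.3%
- k = 2: 2/3 = 66.7%
- k = 3: 3/3 = 100%

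The documents do not give k. The range 0 to 3 covers every possible value, so these figures show what each result weighs, not how often it would happen.

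**Comparison within the SAP**

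For general laboratory values reported as below the lower limit of quantification, SAP section 4 substitutes 0.5 × LLOQ in summary statistics, a non-zero amount. Section 7.2.4 has its own rule for shedding and treats the comparable result as absence.

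**The case against.** The strongest objection is that the harm depends on a laboratory convention that the documents do not give. If BLOQ never includes detectable vector, nothing is misclassified. Naming both terms in 7.2.4 could simply mean that the laboratory uses different labels for blood, urine and CSF. The abbreviation list expands two acronyms; it does not define result states. All of this stands, and it is why the point is conditional and has no frequency attached. It does not rescue the label, since a BLOQ entry alone does not establish non-detection, and the SAP offers nothing further to support that reading.

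A second objection is that the information is not lost. Results are listed by sample type, and SAP section 4 displays below-LLOQ laboratory values as received. With about three subjects, a listing can be read in full. This largely stands, although 7.2.4 does not itself say that shedding entries are listed as received. The listing also does not correct the shift table for someone who reads only the summary.

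A reader might go further and infer that the two clauses of 7.2.4 contradict each other. The text does not support that. The first clause sorts results by how they are recorded, so a result recorded as BLOQ falls under the clause that names it. If a positive value means a quantified number, the clauses are complementary. What remains is an undefined term, which leaves a positive result below the LOQ ambiguous.

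**Conclusion.** The point holds as a limited defect of presentation that should be corrected. Section 7.2.4 reports BLOQ as *Not Detected*, and a result below the quantification limit does not establish absence.

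The stronger effects, a hidden BLOD-to-BLOQ change and an apparent clearance after a quantified result, rest on the assumption that the laboratory uses BLOQ for detected but unquantifiable vector. The documents neither confirm nor exclude this. The frequency cannot be determined; at the minimum enrolment each such result is 1 of 3 subjects for its sample type and visit.

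The consequence is confined to the descriptive shift table and to any by-visit summary built on the same categories. No endpoint or stopping rule uses the classification. A reader might infer that the plan will conceal shedding, or that contact precautions would be set wrongly. The documents do not support either: the rule is stated openly in advance, individual results are listed, and nothing says that precautions depend on this table.

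**What to change.** In SAP section 7.2.4:

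1. Reserve *Not Detected* for results recorded as BLOD.
2. Show BLOQ as a separate category in the shift table and in any by-visit summary. Label it *detected, below quantification* where the assay has an LOD, and *not quantifiable* where it reports against the LOQ only.
3. Define a positive value as a quantified result at or above the LOQ.

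The cost is one or two sentences in the SAP and one extra table category. The change recodes results that are already collected and needs no new samples. The downside is a slightly wider table, in which reported shedding may look a little less favourable.

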7.2.5. Anti-AAV2 Antibody

Number and percentage of subjects with positive and negative antibody (IgG) and neutralized antibody will be presented by visit. A summary table of descriptive statistics will be presented for the observed titer for IgG. A listing of anti-AAV2 antibody parameters will be provided by visit.

7.2.6. T-Cell

A summary table of number and percentage of subjects with positive, negative, and not suitable response will be presented by visit. A listing of T-Cell results will be presented by visit.

7.2.7. Brain MRI

A summary table of number and percentage of subjects with normal/abnormal results will be presented by visit.

A table for shift from baseline will also be provided.

A listing of Brian MRI results including the date performed, impression, overall results and if abnormal, the reason will be specified.

7.2.8. Chest X-Ray

A listing of chest X-Ray including overall X-Ray results (normal, CS abnormal and NCS abnormal) will be provided.

7.3. Vital Signs

A summary table of descriptive statistics will be presented for the observed values and change from baseline for weight, height, temperature, systolic blood pressure, diastolic blood pressure, heart rate, and respiratory rate. Vital sign data will be listed and will include weight, height, temperature, systolic blood pressure, diastolic blood pressure, heart rate, and respiratory rate.

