3. STUDY DESCRIPTION

3.1. Study Design

This is an open-label study in subjects with AADC deficiency. At minimum, 3 eligible pediatric subjects will be enrolled and receive eladocagene exuparvovec at 1.8×10^{11} vg via SmartFlow MR-compatible ventricular cannula in a single operative session. Subjects will receive standard of care for their AADC deficiency during the study. Subjects will undergo Screening and a Baseline Visit before receiving eladocagene exuparvovec by intraputaminal infusion. A Data Safety Monitoring Board (DSMB) will conduct a review of safety data as outlined in the DSMB charter. Review by DSMB will not be required in order to enroll successive subjects. The DSMB will monitor ongoing study results to ensure subject well-being, safety, and study integrity. Subjects will return for regular visits during the course of the study. The length of the study, including the Screening Window, is approximately 63 months (approximately 5 years).

This study's Trial Phase, Extension Phase, and Long-Term Extension Phase are described as follows:

- The primary objectives of the Trial Phase are to assess:
 - the PD of eladocagene exuparvovec treatment by evaluation of HVA levels at 8 weeks after administration
 - the safety of the SmartFlow MR-compatible ventricular cannula for administering eladocagene exuparvovec to pediatric subjects with AADC deficiency.
- The secondary objectives of the Trial Phase are to further assess the PD of eladocagene exuparvovec in subjects with AADC deficiency to further assess the PD of eladocagene exuparvovec in subjects with AADC deficiency using neurotransmitter metabolite assessment and PET analysis.
- The Extension Phase is designed to capture additional clinical information for eladocagene exuparvovec through study evaluations, changes in motor development, AADC-specific- symptoms, and other PD measures. The Extension Phase will be complete at 48 weeks after administration of eladocagene exuparvovec. The additional study evaluations will be assessed as shown in the Schedule of Events in [Table 1](#) and [Table 2](#).
- The Long-Term Extension Phase is designed to capture long-term safety and efficacy data, from subjects treated with eladocagene exuparvovec, through Month 60. Study evaluations for this Phase will be assessed as shown in the Schedule of Events in [Table 3](#).

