4. STUDY POPULATION

4.1. Inclusion Criteria

Subjects will be included if all the following inclusion criteria are fulfilled:

1. Pediatric subjects must have genetically confirmed AADC deficiency with typical clinical characteristics and decreased AADC enzyme activity in plasma.
2. Age range from 1 year to <18 years.
3. Cranium sufficiently developed to allow placement of ClearPoint system for stereotactic surgery.
4. Persistent neurological defects secondary to AADC deficiency despite standard medical therapy (dopamine agonists, monoamine oxidase inhibitor, pyridoxine, or other forms of vitamin B6) in the opinion of the investigator.
5. Unable to ambulate independently (with or without assistive device).
6. Baseline hematology, chemistry, and coagulation values within the normal pediatric laboratory value ranges, unless in the investigator's opinion the out-of-range values are not clinically significant with respect to the subject's suitability for surgery.
7. Subject must test negative for coronavirus disease of 2019 (COVID-19) a maximum of 72 hours prior to receiving gene therapy.

Note: If a subject tests positive for COVID-19 at the Screening or Baseline Visit, he/she will need to have negative test results for 2 weeks (2 weeks since the last positive test result and 2 negative test results a minimum of 14 days apart, with second negative test result no more than 72 hours prior to surgery) before receiving gene therapy. If a COVID-19 test is administered per site policy within 72 hours of the Screening Visit, the results may be used for the AADC-GT-002 study. The COVID-19 test does not need to be repeated after the COVID-19 pre-consent is signed.

8. Subject must be on stable dosage for 3 months prior to baseline for all medications related to treatment of AADC deficiency, including dopamine agonists, monoamine oxidase inhibitors, anticholinergic drugs, and vitamin B6.
9. Females of childbearing potential must have a negative pregnancy test at screening and baseline and agree to abstinence or double-barrier form of contraception for the duration of the study following discharge from the hospital (acceptable methods will be determined by the site).
10. Males sexually active with females of childbearing potential must agree to use a barrier method of birth control during the study following discharge from the hospital.

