7.5.11. Other Safety Assessments

Other safety assessments will include laboratory assessments (complete blood count with differential and platelets, chemistry, and coagulation), physical examinations, vital signs, and height and weight. These assessments will be performed as detailed in [Table 1](#), [Table 2](#), and [Table 3](#).

Viral shedding will be assessed in blood, CSF, and urine as per the Schedule of Events to identify any possible risk of exposure to those who come into contact with a study subject. Anti-AAV2 Antibody testing and T-cell sample collection will be performed as per the Schedule of Events to assess the immune response to gene therapy.

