8.3.3. Analysis of Secondary Endpoints

Observed values and change from baseline in the neurotransmitter CSF metabolites HVA, 5-HIAA, 3-OMD in CSF; brain ¹⁸F-DOPA PET; PDMS-2 total and subscale scores; Bayley-III cognitive and total language subscale scores; EQ-5D-Y scores; body weight; and AADC-specific symptoms will be summarized using descriptive statistics (count, mean, standard deviation, median, minimum, and maximum) or proportion as appropriate for each timepoint.

The number and percentage of subjects who achieve each motor milestone will be summarized by timepoint.

Oculogyric crisis diary data will be summarized by severity, frequency, and proportion and duration of time subjects experienced OGC during the study for selected timepoints, as appropriate.

Respiratory infection rate will be summarized over time.

TEAEs will be summarized as described in Section 8.3.2. The number of subjects who experience dyskinesia, number of dyskinesia episodes, median time to first episode, and summary statistics for duration of dyskinesia events will be provided.

Physical examination, vital signs, MRI, clinical laboratory values, T-cell, anti-AAV2 antibody values, and viral shedding will be summarized by visit, and shift table(s) will be provided if appropriate.

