5.3. Demographic and Baseline Characteristics

A summary table will present descriptive statistics for age at onset, age at diagnosis, age at screening, age at gene therapy, height, weight, body mass index (BMI) and counts and percentages for sex, ethnicity, and race.

Listing for demographic characteristics including date of birth, age at onset, age at diagnosis, age at screening, age at gene therapy, date of treatment, sex, if female whether the subject is of childbearing potential, ethnicity, race, height, weight, and BMI will be provided.

Baseline assessments including genetic testing (method used in obtaining results, DDC gene variant allele 1 and DDC gene variant allele 2), CSF History (5-hydroxyindoleacetic acid, Homovanillic acid, 3-methoxy-4 hydroxyphenylglycol, Neopterin, Biopterin, 3-O-methyldopa, L-Dopa and 5-OH tryptophan), AADC Enzyme activity (Dopamine results, Dopamine range) will be presented.

A summary table of counts and percentages will be provided for genotype (homozygous and heterozygous).

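### SAP 7.3 gives blood pressure, heart rate and respiratory rate no age reference, so the long-term vital-sign summaries cannot separate normal growth from a treatment effect (minor)

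*SAP*

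**What the plan says.** SAP 7.3 is short: "A summary table of descriptive statistics will be presented for the observed values and change from baseline for weight, height, temperature, systolic blood pressure", followed by diastolic pressure, heart rate and respiratory rate, and then a listing of the same items. SAP 4.3 sets baseline as the last value before dosing, and that baseline serves every later visit.

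The protocol places these measurements under other safety assessments (7.5.11), which include "physical examinations, vital signs, and height and weight". Protocol 8.3.3 puts vital signs in a group of variables that "will be summarized by visit, and shift table(s) will be provided if appropriate". SAP 7.3 plans no shift table, and SAP 4.4 declares no change from the protocol's analyses.

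The entry criterion in Protocol 4.1 is "Age range from 1 year to <18 years". Protocol 1.3 rules out a placebo or sham control, and Protocol 3.1 and Table 3 carry follow-up to Month 60.

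SAP 5.3 plans a "Listing for demographic characteristics including date of birth, age at onset, age at diagnosis, age at screening, age at gene therapy", and also sex and height. The data needed for an age reference are therefore collected.

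**The concern.** Blood pressure, heart rate and respiratory rate change with age in healthy children. A raw change over several years contains that growth, and with no control arm and no age standard nothing in the planned output removes it. Pooling adds a second difficulty: a mean over a toddler and an adolescent cannot be compared with any one normal range, and with a minimum of 3 subjects such a mix is quite possible.

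At stake is whether the long-term vital-sign summary can be interpreted. The question is relevant to this product: Protocol 1.1.1 notes that the enzyme is expressed in sympathetic ganglia and the adrenal medulla, and Protocol 7.5.1 provides for managing autonomic dysfunction after surgery.

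**Working it through.** The plan gives no figure on this point to reproduce. The check is a search for a reference, followed by simple arithmetic.

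**1. Is a reference supplied elsewhere?** No. SAP 4 gives generic summary statistics. SAP 4.3.2 mentions age at gene therapy as a covariate, but only in an analysis model, and vital signs have none. No section of either document names a range, percentile, threshold or age stratum for vital signs. SAP 8 leaves the table shells to a separate document that was not available.

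**2. Ages.** 260 weeks / 52 = 5 years. Age at Month 60 runs from 1 + 5 = 6 to under 18 + 5 = 23. Since 18 - 5 = 13, subjects who enter at 13 or older reach 18 by Month 60.

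**3. Volume of data.** In-person visits with vital signs after Dosing Day (the extracted columns of Tables 2 and 3 are shifted, so marks are read as the in-person visits):
- Table 1: Day 3, Weeks 3 and 8 = 3
- Table 2: Weeks 12, 24, 36 and 48 = 4
- Table 3: Weeks 72 and 96, Months 36, 48 and 60 = 5

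The total is 12 visits. With 4 parameters (systolic, diastolic, heart rate, respiratory rate), 12 × 4 = 48 values per child, and 48 × 3 = 144 at the minimum enrolment.

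**4. Growth in the raw change.** Change at time t = treatment effect + (yearly drift × t) + noise. The documents give no drift, so the rates are assumptions: heart rate falls 0 to 6 beats/min per year and systolic pressure rises 0 to 3 mmHg per year. No rate is assumed for respiratory rate or diastolic pressure.

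| Visit | t (years) | Heart rate, growth only | Systolic, growth only |
|---|---|---|---|
| Week 8 | 8/52 | 0 to -0.9 | 0 to +0.5 |
| Week 48 | 48/52 | 0 to -5.5 | 0 to +2.8 |
| Month 60 | 5 | 0 to -30 | 0 to +15 |

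The upper ends hold the top rate constant for the whole period. Growth is negligible at Week 8 whichever rate in the range applies. It could matter from about Week 48.

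**5. Chance flags under a reference-based classification.** For a healthy child who matches the reference, each value falls outside 1st/99th percentile limits with probability 0.02 and outside 5th/95th limits with probability 0.10. If readings are independent:
- One parameter, 12 visits, 5th/95th: 1 - 0.90^12 = 72% with at least one flag
- One parameter, 12 visits, 1st/99th: 1 - 0.98^12 = 22%
- All 48 values, 1st/99th: 1 - 0.98^48 = 62%
- At least one of three children, 1st/99th: 1 - 0.98^144 = 95%

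Positive correlation within a child lowers these. The expected number of flags per child does not depend on correlation: 48 × 0.02 = 0.96, or 48 × 0.10 = 4.8. A count of children with any flagged value would therefore say little, even with wide limits.

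**The case against.** The strongest reply is that nothing important rests on this table. Vital signs appear in neither the safety objectives nor the safety endpoints (Protocol 2.1 to 2.4). With as few as 3 children, safety is read child by child, and the listings allow that. Abnormal findings that need intervention or further work-up become adverse events (Protocol 7.5.2.1), and the medical monitor reviews all of those (7.5.8). This largely stands, and it is why the point is minor. What remains is that a sustained abnormal value needing neither intervention nor work-up would appear only as an unmarked number. The reader would have to apply age norms by hand to 48 values per child.

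It is also fair that the shells may already contain flags; the SAP text does not commit to them. Healthy norms would not isolate a treatment effect either, because AADC medications may continue (Protocol 5.4). Classification removes expected growth, not every other influence.

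Three stronger readings are tempting but unsupported:
- *The SAP contradicts the protocol.* Protocol 8.3.3 makes shift tables conditional, so none is owed.
- *Vital signs were singled out.* A reader might contrast brain MRI, where SAP 7.2.7 says "A table for shift from baseline will also be provided", or entry criterion 6, which asks for "Baseline hematology, chemistry, and coagulation values within the normal pediatric laboratory value ranges". But the SAP's shift tables are for categorical results (also viral shedding and the EQ-5D-Y dimensions). Chemistry, hematology and coagulation (SAP 7.2.1 to 7.2.3) are handled as vital signs are. Criterion 6 is an eligibility screen with investigator discretion, not an analysis reference.
- *The baseline may be a sedated reading.* Table 1 allows sedation on days with imaging or CSF sampling and does not time the vital signs, but nothing says that they are taken under sedation.

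**Conclusion.** The point holds as a minor, supportive safety improvement. At about Week 48 to Month 60, the planned summaries of blood pressure, heart rate and respiratory rate cannot tell normal growth from a treatment effect, and their pooled means have no single normal range. That follows from the entry ages, the absence of a control and the length of follow-up; it does not depend on the assumed drift rates, which only illustrate size and include zero.

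Neither primary endpoint is touched, and the Week 8 vital-sign summaries are essentially unaffected. A reader might infer that a safety signal will be missed. The documents do not support that, since adverse-event capture and individual listings cover the clinically important cases. The conclusion assumes that the unseen shells add no age reference.

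**What to change.** In SAP 7.3:
- Classify each blood pressure, heart rate and respiratory rate value as low, normal or high against one named, prespecified age-specific paediatric reference. Use age at the visit, with sex and height for blood pressure, and adult limits from 18.
- Fix the cut-offs in advance; wide limits such as 1st/99th keep chance flags down.
- Flag out-of-range values in the listing and add a by-visit shift table from baseline, which Protocol 8.3.3 already allows.
- Keep the raw summary as supportive.
- Report flags by visit and by parameter, or require repeated out-of-range values. Do not headline the number of children with any flagged value.

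The cost is SAP wording, one table and a listing flag, with no new data: date of birth, sex, height and vital signs are already collected. The downside is that a reference and cut-offs must be chosen and defended, and some chance flags will remain.
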